## 9 GENERAL CONSIDERATIONS

Data summarization and presentation conventions are documented in a separate document for mock-shells.

### 9.1 Presentation of Summary Statistics

For most summary statistics, data will be analyzed and displayed in tabular format.

Unless otherwise specified, continuous PD hormones ([Section 5.3.2](#)) will be summarized using a 11-point descriptive statistics (i.e., n, mean, standard deviation [SD], median, 25% quartile [Q1],

75% quartile [Q3], minimum, maximum, geometric mean, geometric coefficient of variance [CV%], 95% confidence interval [CI] for geometric mean [including geometric mean ratio and its 95% CI].

All other continuous variables will be summarized using an 8-point descriptive summary (n, mean, SD, median, Q1, Q3, minimum, and maximum) unless otherwise specified.

The same number of decimal places observed in the source data will be presented when reporting minimum and maximum; 1 additional decimal place than in the source data will be presented when reporting mean, median, Q1, Q3, geometric mean, 95% CI; 2 additional decimal places than in the source data will be presented when reporting SD. Geometric CV% will be reported to one decimal place.

All categorical/qualitative data will be presented using the frequency of events and percentages. All percentages will be presented to 1 decimal place, unless otherwise specified. Percentages equal to 100 will be presented as 100% and percentages will not be presented for zero frequencies. For summaries of AEs and CMs, the percentages will be based on the number of subjects who received study drug. All analyses and summaries will be produced using SAS® version 9.4 or higher (SAS Institute Inc, Cary, North Carolina, USA).

### 9.2.2 *Re-Enrolled, Different Cohort*

Re-enrolled subjects will have more than one set of cohort data. Therefore, the summary results by cohort will be summarizing these subjects by unique enrollment experience (per cohort) rather than per subject for summaries of disposition, protocol deviations and study drug exposure. Subjects who re-enrolled into two or more different cohorts will have multiple baseline values for safety and efficacy summaries – a set of baseline values for their first cohort experience, and a set of baseline values for each subsequent cohort experience.

## 9.3 Reporting

Results of statistical analyses will be reported using summary tables, listings, and figures (TLFs). The ICH of Technical Requirements for Pharmaceuticals for Human Use numbering convention will be used for all CSR TLFs.

## 9.4 Definitions and Derived Variables

### 9.4.1 *Screened Subjects*

Subjects who signed an informed consent form are considered Screened Subjects

### 9.4.2 *Enrolled Subjects*

Subjects who receive study drug treatment are considered enrolled subjects.

### 9.4.3 *Study Day*

Study Day, which follows the CDISC SDTM standard, is defined as (Assessment date of first study drug dosing + 1 day), where the assessment date is on or after the date of first study drug dosing; (Assessment date - date of first study drug dosing), where the assessment date is before the date of first study drug dosing.

### 9.4.4 *End of Study Treatment Definition*

A subject in Cohorts 1-3 will have completed the main study treatment period if they completed the Visit 6 (Week 12) Visit. A subject in Cohorts 4-9 will have completed the main study treatment period if they completed the Visit 4 (Week 4) Visit.

### 9.4.5 *End of Study Definition*

A subject will have completed the study if the subject has completed the Follow-up Visit.

### 9.4.6 *Body Mass Index*

Body mass index ( $\text{kg}/\text{m}^2$ ) is derived as  $\text{weight} (\text{kg}) / [\text{height} (\text{m}) \times \text{height} (\text{m})]$ . The most recent height measured will be used in all BMI calculations.

### 9.4.7 *Body Surface Area*

Body surface area is calculated per the Mosteller formula as  $\text{sqrt}((\text{height} (\text{cm}) \times \text{weight} (\text{kg})) / 3600)$ , rounded to one decimal place. The most recent height measured will be used in all BSA calculations.

### 9.4.8 *Tanner Stages*

The Tanner scale is a 5-point scale that is used to describe the onset and progression of pubertal changes in children, with a value of 1 indicating pre-adolescent and a value of 5 indicating mature, adult development. Tanner stages 1-5 are collected for all pediatric patients at 6-month

intervals. Once a Tanner stage of 5 is recorded, no further Tanner staging will be required, and all subsequent values will be recorded as stage 5.

#### 9.4.9 Baseline Values

Baseline values are defined as the last non-missing assessment that is on or prior to the date of the first dose of study drug in each cohort. If the date and time of an assessment are collected, then the date and time are compared against the first dose date and time; otherwise, if only the date of an assessment is collected, the baseline assessment will be the last non-missing assessment collected on or prior to the date of the first dose of study drug. A4, 17-OHP, and ACTH baseline values are defined as the mean of measurements collected between Screening (Visit 1) and Day 1 (Visit 2).

Subjects who re-enrolled into the same cohort, the last-non-missing assessment prior to the second enrollment's first dose of study drug will be used as baseline.

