3.1.2.2. Visit 2 (Day 1)

Visit 2 will be conducted as an outpatient visit during which a supervised first dose of tildacerfont will be administered after completion of a morning meal. The following activities will also be performed during the visit:

- Re-confirm participant meets inclusion/exclusion criteria
- Review concomitant medications for any changes
- Pregnancy test for FOCP (urine)
- For Cohorts 1, 2, 4, 5, 6, 7, 8, and 9 (and 1a if indicated), serial blood samples will be collected at 3 timepoints: pre-dose (prior to GC dosing and tildacerfont dosing), 0.5 to 1.5 hours post-GC and tildacerfont dose, and 3 to 5 hours post-GC and tildacerfont dose. After the pre-dose sample, participants will receive a meal and take their morning GC dose and study drug. Fasting is not required. Blood samples will be used to assess tildacerfont concentrations and to compare to the PBPK model, as well as PD markers including ACTH, 17-OHP, A4, testosterone, and 11KT.
 - Note: Cohorts 1 and 2 (and 1a if indicated) will receive study drug in the mornings for the first 14 days, so they will continue to take study drug at home with a morning meal until Day 14/Visit 3.
- For Cohorts 3 only one pre-dose sample will be drawn, after which participants will receive a meal and their morning GC dose and study drug. They should be observed for approximately 1 hour after receiving study drug.
 - Note: Cohort 3 will only receive the first dose of study drug in the morning to allow clinical observation. They will switch to home dosing with an evening meal on Day 2.
- Vital signs: blood pressure, pulse rate, body temperature, respiration rate, and weight (pre-dose)
- Physical exam (full)
- Safety labs (pre-dose, see [Appendix 1](#) and [Appendix 3](#))
- Dispense study drug (12-week or 4-week supply, depending on cohort)
- Assess for AEs

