- Physical exam (abbreviated/directed)
- Vital signs: blood pressure, pulse rate, body temperature, respiration rate, and weight
- Safety labs (see [Appendix 2](#) and [Appendix 4](#))
- Pregnancy test for FOCP (urine)
- Urinalysis (Weeks 48 and 96 only)
- Pharmacodynamics (ACTH, 17-OHP, A4, testosterone, and 11KT) drawn prior to GC dosing at approximately 8 AM (\pm 1 hour). Fasting is not required.
- Tildacerfont concentration (single sample)

SPR001-205
Spruce Biosciences, Inc.

CLINICAL STUDY PROTOCOL
Version 5.0

- Study drug accountability
- Suicidality Questionnaire- C-SSRS since last visit (participants aged ≥ 6 years only)
- Depression and Anxiety Questionnaires (PROMIS or SWYC depending on age of participant)
- GC dosing adjustments
- Assess for AEs
- Bone age and predicted adult height calculated from X-ray image of left hand and wrist (every 6 months if deemed appropriate by Investigator, see [Appendix 2](#) and [Appendix 4](#)).
- Tildacerfont dose adjustment as needed (based on recommendation of investigator or due to weight-based dosing changes)

4. STUDY POPULATION**4.1. Eligibility Criteria****4.1.1. Inclusion Criteria**

A participant must meet all of the following criteria to be eligible for this study:

1. Male and female participants aged 2- to 10-years (Cohorts 3, 7, and 9), 11- to -17 years (Cohorts 1, 1a, 2, 6, and 8), and ≥ 18 years (Cohorts 4 and 5) at Screening.
2. For participants aged 2 to 5 years, a minimum weight at Screening of 11 kg.
3. Has a known childhood diagnosis of classic CAH due to 21-hydroxylase deficiency (21-OHD) based on genetic mutation in CYP21A2 and/or documented (at any time) elevated 17-OHP and currently treated with hydrocortisone (HC), HC acetate, prednisone, prednisolone, methylprednisolone (or a combination of these). Other types of CAH may be allowed with Sponsor approval.
4. For participants in Cohorts 4-9, $1.2X \text{ ULN} < A4 < 4X \text{ ULN}$. A4 values outside of this range may be allowed with Medical Monitor (MM) approval.
5. A stable dose of GC replacement for ≥ 1 month before Screening without evidence of non-adherence (as assessed by Investigator). Weight-based dose adjustments or stress dosing in the month prior to Screening are not exclusionary but should be discussed with the MM.
6. For participants on mineralocorticoid replacement, a stable dose for ≥ 1 month prior to Screening.

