Cohorts 4, 5, 6, and 7 PD markers and tildacerfont concentration (single sample) ⁸ (also 8 and 9 if indicated)				X	X	X ⁶
A4-based GC dose adjustment ¹⁰				X		
Weight-based tildacerfont dose adjustment	X					
Urinalysis ¹¹	X		X		X	X ⁶

CONFIDENTIAL

Page 81 of 87

SPR001-205

Spruce Biosciences, Inc.

CLINICAL STUDY PROTOCOL

Version 5.0

	Screening ¹	Treatment Period			Early Termination	Safety Follow-up ²
		Day 1	Week 2	Week 4 (EOT)		
VISIT NUMBER	1	2	3	4		5
STUDY DAY	≤14 days before V2	1	14	28		Last dose +30 days
Visit windows			+3 days	±3 days		± 7 days
Vital signs ¹² , body weight	X	X	X	X	X	X ⁶
Physical exam ¹³	X	X	X	X	X	X ⁶
12-lead ECG	X		X ¹⁴		X	X ⁶
Bone age and predicted adult height ¹⁵	X					
C-SSRS ¹⁶	X		X	X	X	X ⁶
PROMIS ¹⁷	X		X	X	X	X ⁶
SWYC ¹⁸	X		X	X	X	X ⁶
Dispense study drug ¹⁹		X				
Study drug accountability			X	X	X	
Clinic drug administration ²⁰		X	X			
Review any AEs		X	X	X	X	X

Abbreviations: 11KT=11-ketotestosterone; A4=androstenedione; ACTH=adrenocorticotropin hormone; AEs=adverse events; ALT=alanine aminotransferase; ALP=alkaline phosphatase; AST=aspartate aminotransferase; CRO=contract research organization; C-SSRS=Columbia–Suicide Severity Rating Scale; ECG=electrocardiogram; eGFR=estimated glomerular filtration rate; EOT=end of treatment; ET=early termination; FOCP=female of childbearing potential; GC=glucocorticoid; GGT=gamma-glutamyl transferase; HIV=human immunodeficiency virus; EP=open-label extension; PD=pharmacodynamics; PK=pharmacokinetics; PROMIS=Patient Reported Outcomes Measurement Information System; 17-OHP=17-hydroxyprogesterone; SWYC=Survey of Well-being of Young Children; T=testosterone.

¹ The Screening Period may be extended as approved by the Sponsor or CRO designee.

² For participants continuing in the EP period, the Safety Follow-up Visit will be 30 days after their last dose in the EP Period.

³ A pregnancy test will be performed at every visit for FOCP. The Screening Visit will include a serum pregnancy test. All subsequent visits will include urine pregnancy tests. Any positive urine pregnancy test must be followed up by a serum pregnancy test for confirmation.

⁴ Labs will be drawn at approximately 8 AM (±1 h) before any morning dose of GC medication.

⁵ Laboratory assessments include: A4, coagulation panel (Screening only), hematology, chemistry (including liver function tests AST, ALT, ALP, GGT, total and direct bilirubin, and total bile acids), thyroid panel. Fasting is not required.

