⁶ As needed based upon safety concerns, per Investigator discretion.

SPR001-205

Spruce Biosciences, Inc.

CLINICAL STUDY PROTOCOL

Version 5.0

⁷ For Cohorts 4, 5, 6, 8, 7, and 9 serial blood samples at 3 timepoints to assess PD (ACTH, 17-OHP, A4, testosterone, 11KT, cortisol) and tildacerfont concentrations following the morning (1st) dose: pre-dose (prior to GC dosing and tildacerfont dosing), 0.5 to 1.5 hours post GC and tildacerfont dose, and 3 to 5 hours post-GC and tildacerfont dose. Serial samples should be attempted in all cases but may be declined in Cohort 7 & 9 at Investigator's discretion (e.g., unable to establish IV, behavioral challenges impede collection and risk other assessments).

⁸ For Cohorts 4, 5, 6, 8, 7, and 9 single blood sample to assess PD (ACTH, 17-OHP, A4, testosterone, and 11KT) and cortisol and tildacerfont concentration. Pre-dose at approximately 8 AM (± 1 h), prior to GC dosing and tildacerfont dosing.

⁹ Tildacerfont concentration collected prior to the morning tildacerfont and GC dose. Fasting is not required.

¹⁰ In all cohorts, GC dose (frequency or total daily dose) may be adjusted based on A4 levels collected at Week 4 (for those participants continuing in the optional EP). If a change in GC is warranted by the A4 algorithm, sites will contact participants by telephone after receipt of results (within approximately 2 weeks) after each applicable study visit.

¹¹ Urinalysis should include the following: specific gravity, pH, glucose, protein, blood, ketones, bilirubin, urobilinogen, nitrite, by dipstick. Microscopic examination should be obtained if blood or protein is abnormal. For visits in which tildacerfont is administered, urinalysis should be performed pre-dose.

¹² Systolic and diastolic blood pressure, pulse rate, body temperature, and respiration rate. Height will only be collected at Screening.

¹³ Full physical exam is performed at Visit 2, EOT, and the ET Visit; an abbreviated/directed physical exam is performed at all other visits.

¹⁴ Day 1 ECGs are conducted pre-dose. Day 14 ECG is dose independent, as participants should be at steady state.

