## **9.5 Analysis Windows**

Protocol-specified visits and unscheduled clinical visits may be used to capture missed or partially completed clinical visits; therefore, analysis visits and their windows are defined using Study Day (See [Section 9.4.3](#)). For the purposes of data analysis and summary, assessments and

measurements will be preferentially flagged based on the collection date/time that is closest to the protocol-scheduled time point (or target Study Day). Analysis visit windows are presented in **Table 7**.

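### SAP 9.4.9 does not restrict the A4, 17-OHP and ACTH baseline mean to pre-dose samples, so two Day 1 post-dose draws enter it in the serial-draw cohorts

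*SAP*

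**What the plan says.** SAP 9.4.9 opens with a general rule: baseline is the last non-missing assessment on or before first dose, and "If the date and time of an assessment are collected, then the date and time are compared against the first dose date and time". It then gives three hormones a definition of their own: "A4, 17-OHP, and ACTH baseline values are defined as the mean of measurements collected between Screening (Visit 1) and Day 1 (Visit 2"). The closing sentence, on participants re-enrolled in the same cohort, again names a limit before first dose.

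Protocol 3.1.2.2 sets the Day 1 sampling. Cohorts 1, 1a, 2 and 4-9 give one sample before GC and tildacerfont, then two more at "0.5 to 1.5 hours post-GC and tildacerfont dose, and 3 to 5 hours post-GC and tildacerfont dose". Appendix 3, footnote 7, confirms for Cohorts 4-9 that these are "serial blood samples at 3 timepoints to assess PD (ACTH, 17-OHP, A4, testosterone, 11KT, cortisol) and tildacerfont concentrations"; Appendix 1, footnote 7, does the same for Cohorts 1 and 2. Cohort 3 gives one pre-dose sample only.

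On Screening values, the PD rows of the schedules in Appendices 1 and 3 start at Day 1. Cohorts 4-9 nevertheless have a Screening A4: inclusion criterion 4 (Protocol 4.1.1) needs one, and Appendix 3, footnote 5, reads "Laboratory assessments include: A4, coagulation panel (Screening only), hematology, chemistry". The matching footnote in Appendix 1 does not list A4.

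From Week 4 on, the hormones are single samples taken before GC at about 8 AM (Protocol 3.1.2.4 to 3.1.2.6).

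**The concern.** A baseline that mixes samples taken before and after GC and study drug is compared with follow-up values taken only before GC. Any acute effect of the morning GC dose, of the first tildacerfont dose or of time of day then enters the baseline and appears as treatment effect with the opposite sign.

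The A4 baseline feeds:

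- the A4 component of the composite responder (SAP 13.1.1);
- reduction in A4 at Week 4 among those with elevated baseline (SAP 13.1.2);
- membership of the Elevated Baseline PD (EBPD) set (SAP 8), and through it the denominator for normalization among those with elevated baseline;
- the baseline A4 subgroup (SAP 10.7).

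For all three hormones it also feeds change from baseline, the geometric mean ratios and the proportions with any or at least 50% reduction.

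Cohort 3 keeps a purely pre-dose baseline, so cohorts shown side by side would have baselines built differently. The same can happen within Cohorts 7 and 9, where serial draws may be declined.

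**Working it through.** **No stated figure to reproduce.** SAP 7 says no formal sample size calculation was performed, and neither document gives a post-dose hormone profile. The check is therefore a count of draws followed by conditional arithmetic.

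**Share of post-dose values.**
- Day 1 only (17-OHP and ACTH per the schedules; A4 in Cohorts 1, 1a and 2): 2 of 3.
- Day 1 plus one Screening value (A4 in Cohorts 4-9): 2 of 4.
- The synopsis says PD samples are taken at all other visits. If that includes Screening, the four-draw case applies more widely.

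**Reach in planned places (Protocol Table 1).** Cohorts 1, 1a and 2: 5 + 5 + 5 = 15. Cohorts 4-9: 5 + 10 + 5 + 5 + 10 + 10 = 45. Total 60 of up to 70; the other 10 are Cohort 3. Of the 45, 15 (Cohorts 7 and 9) may decline serial draws.

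**Bias.** Set the Screening and Day 1 pre-dose levels to 1, and let r be the assumed ratio of each post-dose draw to pre-dose. The baseline relative to a pre-dose baseline is k = (2 + 2r)/4 with four draws and k = (1 + 2r)/3 with three. Then:
- apparent change = (true ratio)/k - 1;
- pre-dose A4 needed to enter the EBPD set = 1/k, in multiples of ULN;
- true fall needed to count as at least 50% reduction = 1 - 0.5k.

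| Draws | r | k | No true change reads | True 20% fall reads | EBPD threshold (xULN) | True fall needed for 50% |
|---|---|---|---|---|---|---|
| 4 | 0.9 | 0.950 | +5.3% | -15.8% | 1.05 | 52.5% |
| 4 | 0.8 | 0.900 | +11.1% | -11.1% | 1.11 | 55.0% |
| 4 | 0.7 | 0.850 | +17.6% | -5.9% | 1.18 | 57.5% |
| 3 | 0.9 | 0.933 | +7.1% | -14.3% | 1.07 | 53.3% |
| 3 | 0.8 | 0.867 | +15.4% | -7.7% | 1.15 | 56.7% |
| 3 | 0.7 | 0.800 | +25.0% | 0.0% | 1.25 | 60.0% |

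With r = 1.0, k = 1 and there is no systematic bias. With r = 1.1, no true change reads as 1/1.05 - 1 = -4.8% (four draws) or 1/1.067 - 1 = -6.2% (three): a false reduction.

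A steeper decline is also possible. With ratios of 0.8 at the first post-dose draw and 0.4 at the second, k = (1 + 1 + 0.8 + 0.4)/4 = 0.80 with four draws, and a participant at 1.2xULN gets a baseline of 0.96xULN.

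**Responder illustration (A4, four draws, true 20% fall).** Two million simulated participants, with independent lognormal day effects S (Screening), D (Day 1) and F (follow-up). As written, a responder has 0.8F < (S + D(1 + 2r))/4; with a pre-dose mean, 0.8F < (S + D)/2. The log-SD is an assumption.

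| Log-SD | Pre-dose mean | r = 1.0 | r = 0.9 | r = 0.8 | r = 0.7 |
|---|---|---|---|---|---|
| 0.2 | 83% | 82% | 76% | 69% | 61% |
| 0.3 | 75% | 73.5% | 69% | 64% | 58% |
| 0.5 | 68% | 66% | 63% | 60% | 57% |

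The r = 1.0 column shows that about 1 point of each drop comes from giving Day 1 three quarters of the weight, not from post-dose bias.

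**Does another SAP section supply the restriction?** In SAP 9.5, "analysis visits and their windows are defined using Study Day", so all Day 1 draws share a window. The flag is "preferentially flagged based on the collection date/time that is closest to the protocol-scheduled time point"; it does not name the pre-dose draw and does not clearly override an explicit mean. SAP 15, on changes from the protocol, is silent.

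**The case against.** The hormone sentence sits in the paragraph that defines baseline as on or before first dose, so it could be read as changing only the statistic (mean in place of last value) with the timing rule intact. That is a fair reading and probably the intended one. But the sentence sets its own window by visits and omits the condition stated both before and after it. At best the text allows two baselines, and the literal one is wrong. Data conventions are also held in a separate mock-shell document that cannot be checked here.

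The magnitude rests on assumed ratios and variability. That stands: neither size nor direction can be taken from the documents.

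The practical effect is limited, and this also stands. At log-SD 0.3 the simulated shift is about 6 to 16 percentage points, or 0.3 to 0.8 of a participant in a cohort of five, and the planned exact interval for 4 of 5 responders already runs from 28% to 99%. Efficacy is descriptive, and if post-dose values are lower the error works against the drug.

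Reach is a ceiling. Cohort 1a, Cohorts 8 and 9 and the extra groups of five are optional; Protocol 1.2.3 already reports 30 participants in Cohorts 1-3 against 25 planned places; and SAP 13 excludes data collected under Protocol v3.0 from efficacy.

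EBPD misclassification is less likely in Cohorts 4-9, where entry requires A4 above 1.2xULN, although "A4 values outside of this range may be allowed with Medical Monitor (MM) approval". The thresholds of 1.05 to 1.18xULN stay below that limit, but the steeper decline shown above does not, so the protection depends on the assumed ratio. The baseline of the A4/T ratio is not defined separately, so the effect there is uncertain.

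**Conclusion.** The concern holds. As written, SAP 9.4.9 puts two post-GC, post-tildacerfont draws into the A4, 17-OHP and ACTH baseline for Cohorts 1, 1a, 2 and 4-9, and no other SAP section removes them. SAP 4 makes the SAP govern where it and the protocol differ on planned analyses, so the sentence should be correct as it stands.

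The structural fact, that half to two thirds of the averaged values are post-dose, comes directly from the documents. The numerical effect does not. For post-dose levels of 70% to 90% of pre-dose, the baseline is 5% to 15% low with four draws and 7% to 20% low with three; the effect is nil at equality and reverses if post-dose levels are higher.

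Unaffected are the primary safety endpoint, Cohort 3, same-cohort re-enrollers (who have their own pre-dose rule), testosterone's own baseline and participants without post-dose PD draws. The last group includes those who decline in Cohorts 7 and 9 and possibly those re-consented from amendment 3, for whom the post-dose concentration draws are waived.

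This should be fixed before database lock. It touches secondary endpoints and an analysis set, but in small descriptive cohorts.

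**What to change.** Replace the hormone sentence in SAP 9.4.9 with wording such as: *Baseline for A4, 17-OHP and ACTH is the mean of the samples taken before the morning GC dose and before the first tildacerfont dose (scheduled at about 8 AM) at Screening, where taken, and Day 1. Day 1 post-dose samples are excluded.* The dose-relative condition should decide inclusion; the clock time is descriptive, so a pre-dose sample slightly outside the 8 AM window is not lost. This agrees with Protocol 5.3.1.1, which has participants delay morning GC at every visit, including Screening.

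It would help to say in the same place which baseline the A4/T ratio uses, since testosterone stays under the general rule.

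Cost: one SAP sentence and a filter on nominal sample time point in the analysis dataset. No new data, visits or samples are needed.
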